10. EXPERIMENTAL PLAN

10.1 OVERVIEW

This study will be conducted in accordance with U.S. Code of Federal Regulations, the Declaration of Helsinki, ISO 14155 and all other applicable laws and regulations. The study will not begin until IRB approvals have been obtained.

This study will be a post-market, prospective, multicenter, bilateral, randomized, open-label, cross-over, comparative clinical study conducted at up to 7 sites in the U.S. Approximately 140 subjects will be randomized and bilaterally implanted, resulting in approximately 110 evaluable subjects (55 in the study arm and 55 in the control arm).

After signing the informed consent, subjects meeting all inclusion and exclusion criteria will be randomized to either the Study group or the Control group.

The duration of study participation is from the initial Preoperative Visit #1 to a final visit at 3 months or 4 months after the second-eye cataract surgery, depending upon the subject's randomized group assignment. All subjects in both arms are intended to have bilateral cataract surgery. The subjects randomized to Study group will undergo preoperative LipiFlow treatment and the subjects randomized to Control group will not receive preoperative LipiFlow treatment. Three months postoperatively, both groups will be evaluated for clinical outcomes and the Control group will receive LipiFlow treatment as the cross-over group. The Control group will be evaluated at 4 months postoperative for clinical outcomes.

Key data collection for all subjects/eyes includes distance visual acuities, manifest refraction, contrast acuity, keratometry, biometry, corneal topography, visual symptoms, Meibomian gland evaluation, biomicroscopic slit-lamp findings, complications and adverse events. A chart summary of all examination or treatment procedures required at each study visit is provided in **Appendix B**. If needed, specific equipment necessary to perform the required procedures will be supplied for the duration of the study (**Appendix C**). The study visit schedule is described in Section 10.2.

Although the study is not masked, to maintain consistency, it is recommended that a single individual (study technician or coordinator designated by the investigator) conduct all study-related vision testing, although a back-up person should also be designated and trained.

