10.2 VISIT SCHEDULE

The study visit schedule for all study subjects is outlined in **Table 1**.

Subjects randomized to the **Study Group** will undergo a minimum of the following four study visits (with visit windows shown in parentheses):

- 1) Preoperative Visit #1, including LipiFlow treatment (may occur on the same day or within 1 week of Visit #1)
- 2) Preoperative Visit #2 (2 - 4 weeks after LipiFlow treatment)
- 3) 1 Month Postop (30 - 60 days after cataract surgery on second eye)
- 4) 3 Months Postop (10 to 14 weeks after cataract surgery on second eye)

Subjects randomized to the **Control group** will undergo a minimum of the following five study visits (with visit windows shown in parentheses):

- 1) Preoperative Visit #1
- 2) Preoperative Visit #2 (2 - 4 weeks after Preoperative Visit #1)
- 3) 1 Month Postop (30-60 days after cataract surgery on second eye)
- 4) 3 Months Postop (10 to 14 weeks after cataract surgery on second eye), including the crossover LipiFlow treatment, which should occur within 0 - 7 days after the 3 months postoperative visit
- 5) 4 Months Postop (4 to 6 weeks after receiving crossover LipiFlow treatment)

Unscheduled visits may be conducted as necessary at the discretion of the investigator for medically-indicated follow-up.

Table 1: Visit Schedule

NAME OF VISIT	GROUPS	PROCEDURES	VISIT WINDOW
Preoperative #1	All	Informed Consent, Screening, Baseline, Randomization and Enrollment	Per site practice
LipiFlow Treatment	Study Group	LipiFlow treatment	LipiFlow treatment can occur on the same day or within 1 week of Visit #1
Preoperative #2	All	Preoperative	Study Group: 2-4 weeks after LipiFlow treatment; Control Group: 2-4 weeks after Visit #1
1 Month Postop	All	1 month postoperative	30-60 days after cataract surgery on second eye
3 Months Postop	All	3 months postoperative; The crossover Control group will receive LipiFlow treatment within 0-7 days after the 3 months postoperative visit	10 to 14 weeks after cataract surgery on second eye
4 Months Postop	Crossover Control Group Only	4 months postoperative	4 to 6 weeks after receiving crossover LipiFlow treatment

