- Residual refractive error resulting in a secondary surgical intervention
- Retained lens material resulting in secondary surgical intervention

NOTE 1: Wound burps during the first week postoperatively, suture removal, planned blepharoplasty and Nd:YAG capsulotomy (for PCO) are not considered adverse events for this study.

NOTE 2: Persistent corneal edema, IOP increase, and uveitis/iritis will be considered serious according to the guidelines listed in **Appendix U**. (i.e., persistent IOP increase of 10 mm Hg from baseline to at least 25 mm Hg; corneal edema resulting in BCDVA of 20/40 or worse at 1 month or later; and Grade 1+ uveitis/iritis longer than 3 months.

Unanticipated Adverse Device Effect (UADE)/Unanticipated Serious Adverse Device Effect (USADE)

Any UADE (USA 21CFR 812.3(s)) or USADE (ISO 14155) is defined as any serious adverse effect on health or safety or any life-threatening problem or death caused by, or associated with, a device, if that effect, problem, or death was not previously identified in nature, severity, or degree of incidence in the investigational plan (i.e., this protocol), application (including a supplementary plan or application), or risk assessment, or any other unanticipated serious problem associated with a device that relates to the rights, safety, or welfare of subjects.

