Financial Disclosure(s): The author(s) have made the following disclosure(s): J.T.H.: Consultant – Abbott Medical Optics (Milpitas, CA); Alcon Laboratories, Inc. (Fort Worth, TX); Carl Zeiss, Inc. (Oberkochen, Germany); Oculus, Inc. (Wetzlar, Germany); Consultant and Equity Owner – AcuFocus, Inc. (Irvine, CA); ArcScan (Morrison, CO); Elenza (Roanoke, VA); Visiometrics (Barcelona, Spain). A.G.: Consultant – Abbott Medical Optics, LensAR (Orlando, FL); Medicem (Cheshire, UK); Refocus Group (Dallas, TX); Tracey Technologies (Houston, TX); Vista Ocular (North Canton, OH); Consultant and Equity Owner – Encore Vision (Fort Worth, TX); LensGen (Irvine, CA); PowerVision (Belmont, CA).

The mention of commercial products, their sources, or their use in connection with material reported herein is not to be construed as either an actual or implied endorsement of such products by the Department of Health and Human Services (DHHS). The following authors: M.E.T., G.H., T.N., E.R., D.C., and M.E. are employees of the U.S. Government and prepared this work as part of their official duties. Title 17, USC, § 105 provides that copyright protection under this title is not available for any work of the United States Government. Title 17, USC, § 101 defines a U.S. Government work as a work prepared by a military service member or employee of the U.S. Government as part of that person's official duties.

Reports

Table 1. Postoperative Adverse Event Definitions for Intraocular Lenses

Adverse Event	Definition
Chronic anterior uveitis	Persistent anterior segment inflammation characterized by grade 1+ cell or greater using SUN criteria ³
Clinically significant cystoid macular edema	Macular edema diagnosed by clinical examination and adjunct testing (e.g., OCT, FA) resulting in BCDVA of $\leq 20/40$ at ≥ 1 mo
Corneal edema	Corneal swelling (stromal or epithelial) resulting in BCDVA of $\leq 20/40$ at ≥ 1 mo
Endophthalmitis	Intracocular inflammation requiring diagnostic vitreous tap and intracocular antibiotics
Mechanical pupillary block	Shallowing of anterior chamber due to obstruction of aqueous humor flow from the posterior to anterior chamber through the pupil by the crystalline lens, vitreous face, or implanted device
Increased IOP	Elevation of IOP by ≥ 10 mmHg above baseline to a minimum of 25 mmHg
Rhegmatogenous RD	Partial or complete RD associated with retinal tear

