#### 4.2.4 RATE OF ADVERSE EVENTS/MEDICAL AND/OR LENS FINDINGS

The frequency and proportion of eyes with optical/visual, medical and lens complications will be reported over time. The type and rates of adverse events will be summarized for both study group eyes and control group eyes.

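### Adverse events are compared by arm over unequal follow-up (day 70–98 in Study, day 98–147 in Control), which matters most for uveitis/iritis classed as serious by its duration

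*Protocol*

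**What the plan says.** **Length of follow-up.** Protocol 10.1 sets the end of participation at "a final visit at 3 months or 4 months after the second-eye cataract surgery, depending upon the subject's randomized group assignment". Section 10.2 gives the windows. Both arms have "3 Months Postop (10 to 14 weeks after cataract surgery on second eye", and this is the last scheduled Study visit. Control then receives the crossover LipiFlow treatment, "which should occur within 0 - 7 days after the 3 months postoperative visit", and returns for "4 Months Postop (4 to 6 weeks after receiving crossover LipiFlow treatment".

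**Seriousness of uveitis/iritis.** Protocol 11.1 NOTE 2 says that persistent corneal edema, raised IOP and "uveitis/iritis will be considered serious according to the guidelines listed in" Appendix U. For inflammation it then spells the guideline out as "Grade 1+ uveitis/iritis longer than 3 months". The matching entry in Appendix U, Table 1 reads "Persistent anterior segment inflammation characterized by grade 1+ cell or greater using SUN criteria"; as printed it gives no number of months. The general SAE criteria earlier in 11.1 do not depend on duration.

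**Analysis.** SAP 4.2.4: "The type and rates of adverse events will be summarized for both study group eyes and control group eyes". Neither that section nor the SAP table listing (Appendix I) states a common cut-off, an exposure adjustment, or a rule for events still open when a subject exits.

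**The concern.** A by-arm event rate is interpretable when both arms are watched for the same length of time under the same conditions. Here Control is examined once more, four to seven weeks after the 3-month visit and after its own LipiFlow treatment. Any event that arises or is first noticed in that period, including the transient lid and ocular surface reactions that Protocol section 17 lists as possible after LipiFlow, is added to the Control rate with no Study counterpart in the same postoperative period.

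A duration rule sharpens the problem. The 3-month threshold falls inside the window of the last Study visit, so the same persisting inflammation may stay non-serious in a Study eye and become serious in a Control eye only because the latter is seen again. The corneal edema criterion in the same NOTE, set at 1 month or later, can be met on the schedule the arms share.

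The direction favors preoperative LipiFlow. What is at stake is the fairness of the between-arm safety summary. No efficacy endpoint is affected.

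**Working it through.** The plan states no figure for this point, so there is none to reproduce. The check is date arithmetic on the visit windows.

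**Inputs.** Threshold: longer than 3 months (NOTE 2), taken as 365.25/12 × 3 = 91.3 days, with 90 days as a sensitivity value. Windows: Protocol 10.2. Assumptions: visits and the crossover treatment are spread evenly over their windows, and inflammation lasts from onset to the last scheduled visit. The interval between the two surgeries is not given, so it is varied.

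**Step 1, last scheduled visit (days after second-eye surgery).**
- Study: 10 × 7 = 70 to 14 × 7 = 98.
- Control: 70 + 0 + 28 = 98 to 98 + 7 + 42 = 147, i.e. 14 to 21 weeks.
- Extra time in Control after the 3-month visit: 0 + 28 = 28 to 7 + 42 = 49 days.

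**Step 2, latest second-eye onset that can still qualify** (latest visit day minus threshold).
- Study: 98 − 91.3 = 6.7, so about day 6.
- Control: 147 − 91.3 = 55.7, so about day 55.
- A Control subject on the shortest schedule (day 98) is no better placed than a Study subject on the longest.

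**Step 3, chance that a persisting second-eye inflammation has passed the threshold at the last scheduled visit.** Study share = (98 − onset − threshold)/28, limited to 0–1. For onset on day 0: (98 − 0 − 91.3)/28 = 24%. The Control share comes from simulating the sum of the three windows (one million draws).

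| Onset day | Study, 91.3 d | Study, 90 d | Control, 91.3 d | Control, 90 d |
|---|---|---|---|---|
| 0 | 24% | 29% | 100% | 100% |
| 7 | 0% | 4% | 100% | 100% |
| 14 | 0% | 0% | 98% | 99% |
| 30 | 0% | 0% | 54% | 59% |

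**Step 4, first-operated eyes.** Add the inter-eye gap g to the time available: (98 + g − onset − 91.3)/28, with onset counted from that eye's own surgery. For g = 7 and onset on the day of surgery: 13.7/28 = 49%.

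| Assumed gap | Study, onset day 0 | Study, onset day 14 | Control, either onset |
|---|---|---|---|
| 7 days | 49% | 0% | 100% |
| 14 days | 74% | 24% | 100% |
| 21 days | 99% | 49% | 100% |
| 28 days | 100% | 74% | 100% |

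**Step 5, one illustration.** Two second eyes have grade 1+ iritis from day 7, and both are seen on day 84. The Study subject exits with 84 − 7 = 77 days recorded. The Control subject is treated that day and seen on day 84 + 35 = 119, with 119 − 7 = 112 days recorded. Only the second passes the threshold on scheduled visits.

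**Step 6, can the Study event be updated later?** Section 11.5 wants every event managed and watched until it resolves. Repeat SAE/ADE forms, however, are specified only for events that are serious or device-related. Section 11.3 has other events recorded on the form for the visit at which they come to notice. Section 10.8 provides unscheduled-visit forms within the study period, and the follow-up after exit in section 10.7 concerns lens removal and other serious events. An unrelated iritis below the threshold at Study exit therefore has no clearly stated route back into the data as serious.

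**The case against.** The strongest reply is that the last scheduled visit does not end safety observation. Section 11.5 covers every adverse event in both arms. If monitoring shows that an inflammation has lasted more than 3 months, it becomes serious and the SAE reporting rules apply on detection. Device-related inflammation has a follow-up form whatever its duration. This largely stands. What remains is uncertainty about how a late change of status in an unrelated event would be captured after Study exit.

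Some stronger readings are tempting, and the documents do not support them:

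- *Uveitis can be serious only after 3 months.* The general SAE criteria in 11.1 (for example, a threat to sight) apply at any duration. The duration route matters only for inflammation that meets none of them.
- *Persistent uveitis will be an SAE almost only in Control.* That takes the second-eye figures as if they covered all eyes and ignores section 11.5. The SAP analyses all implanted eyes, and with a gap of 21–28 days and onset at surgery the first-eye difference nearly vanishes. Even in Control, a second-eye onset on day 30 qualifies only about half the time.
- *The safety table will display this contrast.* SAP 4.2.4 and Appendix I name neither a persistent-uveitis row nor a serious/non-serious split. The Study eye's iritis still counts as an adverse event, and medical findings are already reported over time.
- *NOTE 2 contradicts Appendix U.* The Appendix U entry says persistent and defers to SUN criteria, whose content is not in the documents. The two need reconciling, but a contradiction is not shown.

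It is also fair to say that the between-arm bias comes from unequal follow-up. With a common cut-off, the 3-month rule would be insensitive for second eyes, but equally so in both arms.

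**Conclusion.** The point holds in a limited form. By-arm adverse event rates are planned over scheduled periods that differ by 28–49 days per subject beyond the shared 3-month visit, and the extra Control period is not comparable because it includes LipiFlow treatment. For second-eye uveitis/iritis that is serious by duration alone, the qualifying onset period on scheduled visits is about 6 days in Study and up to about 55 days in Control. For first-operated eyes the difference ranges from large to none over the assumed gaps of 7–28 days.

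These figures rest on evenly spread visits, inflammation that persists to the last visit, and classification at scheduled visits only. The documents give no incidence of uveitis/iritis, so neither an expected count nor an overall ratio between arms can be stated, and the absolute number may be small. The summary is descriptive, with no safety test attached. The change is still worth making because the direction favors the treated arm and the repair is nearly free.

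**What to change.** In SAP 4.2.4 and the matching Appendix I row:

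1. Make the between-arm comparison of adverse events and serious adverse events through the 3-month visit in both arms, closing it when that visit's examinations are complete and before any crossover treatment.
2. Tabulate separately the Control events that arise, or first qualify as serious, after that visit.
3. List events ongoing at the 3-month visit by arm, with duration to date, so that an open Study event remains visible whatever its later classification.

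In Protocol 11.1, the sponsor should reconcile the NOTE 2 duration with Appendix U and with the length of Study-arm follow-up. No clinical definition is proposed here. In particular, no substitute criterion built on the 1- and 3-month visits is suggested: their windows (days 30–60 and 70–98) allow visits only 70 − 60 = 10 days apart, and the choice is a clinical one.

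**Cost.** SAP wording, one extra table and one listing. No new visit or examination is needed, since adverse events and slit-lamp findings are already collected at the 3-month visit. The downside is that the main between-arm table will show fewer Control events, and events serious by duration will be few in both arms.

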11.2 PRODUCT COMPLAINT/DEVICE DEFICIENCY DEFINITION

A product complaint/device deficiency is defined (21 CFR 820.3(b) and ISO 14155) as any alleged deficiency related to the identity, quality, durability, reliability, safety, effectiveness, or performance of a device. This may include malfunctions, use error and inadequacies in labeling. Product complaints can pertain to any marketed JJSV device being used in the study. The investigator is to assess whether the deficiency could have led to a serious adverse event without suitable action or intervention or under less fortunate circumstances.

11.3 ADVERSE EVENT AND COMPLAINT REPORTING REQUIREMENTS

All adverse events and any complaint encountered using any JJSV product, regardless of severity and whether or not attributed to the study device(s), are to be reported to JJSV and recorded on the case report form corresponding to the visit during which awareness of the event occurred. Adverse events are also to be reported to the reviewing IRB as per the IRB's reporting requirements. If required, adverse events will be reported to the appropriate regulatory agencies (e.g., FDA) according to all applicable laws and regulations.

Reporting of adverse events shall follow the USA Code of Federal Regulations for sites in the USA. General guidelines are provided below:

Adverse Event Reporting

An adverse event that is not serious or device-related is to be reported to JJSV in a timely manner. Notification of non-serious and non-device related adverse events will occur by recording events on the CRF when noted. Such adverse events are also to be reported to the reviewing IRB per their reporting requirements.

Complaints/Device Deficiency Reporting

A general product complaint or device deficiency is to be reported to JJSV in a timely manner. Notification of complaints/device deficiencies will occur by either recording complaints on the CRF when the complaint occurred (e.g. operative form) or by a phone call to the Sponsor. Any device deficiency that could have led to a serious adverse event without suitable action or intervention, or under less fortunate circumstances, must be reported to the sponsor immediately (no later than 48 hours after detection). Device deficiencies that could have led to a serious adverse event should also be reported to the investigator's IRB per their reporting requirements.

Serious and/or Device-Related Adverse Event Reporting

Serious and/or device related events (ADEs) are to be documented using the Serious Adverse Event/Adverse Device Effect (SAE/ADE) CRF. In the event of a serious adverse event (SAE), which may or may not be related to use of the study device, JJSV must be notified immediately (no later than 48 hours after detection). Any SAE is to be reported by phone (and/or email) and by submitting the completed SAE/ADE CRF. Any SAE or device-related AE should also be reported to the investigator's IRB per their reporting requirements.

Unanticipated Adverse Device Effect (UADE)/Unanticipated Serious Adverse Device Effect (USADE) Reporting

If during the study, a serious adverse event occurs that may reasonably be regarded as device-related and was not previously expected in nature, severity, or degree of incidence, the investigator is to report the UADE/USADE to JJSV within 48 hours, and to the investigator's IRB as soon as possible (and no later than 10 working days after learning of the event for sites in the USA).

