If the LipiFlow treatment is performed on the same day as Preoperative Visit #1, the medical/ophthalmic history and slit lamp evaluation do not need to be repeated before treatment. In this case, the Investigator must review the baseline history and slit lamp exam information prior to treatment to ensure no contraindication to LipiFlow treatment is present. If the LipiFlow treatment visit is performed on a different day from Preoperative visit #1, the Investigator or designee documents any changes to medical/ophthalmic history and performs a slit lamp evaluation to determine if an ocular adverse event is present prior to treatment. If the subject has an active ocular adverse event, the LipiFlow treatment should not be performed at this visit.

The Investigator or designee cleans the lid margin (**Appendix E**) and then performs treatment with the LipiFlow system per the LipiFlow System Instructions for Use. The Investigator documents any problems with the LipiFlow system during treatment. The Sponsor will investigate any reported problem with the LipiFlow system.

The Investigator or designee performs slit-lamp evaluation after LipiFlow treatment to check for any adverse events. At the completion of the exam, the subject is instructed on how to perform blinking exercises (**Appendix F**) for 1 month after treatment to facilitate the flow of oils from the meibomian glands into the tear film. The subject is advised to return for Pre-Operative Visit #2, which must be scheduled 2 - 4 weeks after the LipiFlow treatment.

At the completion of Preoperative Visit #1, the subject is reminded not to use any MGD or dry eye prescription medications or other treatments during the study (except for pre-existing OTC artificial tears, ocular lubricants, ointments, emollients or ω-3 dietary supplements). The dosage and frequency of any pre-existing use of OTC products upon study entry must be documented in the subject's medical record and in the study case report forms. Except for LipiFlow treatment, no other MGD or dry eye treatment is prescribed or administered to subjects throughout the study.

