10.7 EXIT OF SUBJECTS

An Exit Case Report Form will be completed for all subjects, either when they complete the study or if they exit early.

It is the responsibility of the investigator to provide complete follow-up data to JJSV for each subject, and every attempt should be made to gather that complete follow-up data for all subjects enrolled as missing data can have a negative effect on the study results. Patients who will be traveling, relocating or otherwise unavailable for postoperative follow-up visits should not be chosen for this clinical study.

A subject will be considered a “screen failure” if he/she does not meet the inclusion/exclusion criteria or if consent is withdrawn prior to randomization.

A subject will be considered “discontinued prior to treatment” if the subject is randomized but does not undergo bilateral LipiFlow treatment (study group) or receive a Symfony lens for various reasons including: the planned implant being aborted due to surgical complications, the subject withdrawing consent prior to treatment, or the subject died prior to treatment. If a subject receives at least one Symfony lens, he/she is to be followed according to the protocol.

A subject will be “discontinued” from the study if one study lens (if implanted unilaterally) or both study lenses (if implanted bilaterally) are removed or if the subject dies.

Subjects will be considered “lost-to-follow-up” from the study only if irretrievably lost for unavoidable reasons such as: subject moved/unable to locate, subject uncooperative/refuses further study participation, subject ill/unable to travel. In the event of subject relocation, efforts must be made by the investigator to secure follow-up information (i.e., slit-lamp findings and general visual acuity, etc.) from the subject’s new physician.

If a subject is exited early from the study, the investigator will send an Exit Case Report Form to JJSV indicating the reason for study exit. In the event of a lens removal or other serious adverse event, the subject may be exited from the study; however, efforts must be made by the investigator to follow the subject until resolution of the adverse event.

Following study completion or early exit, all study subjects are to be instructed to undergo regular eye examinations at least yearly and also to return to their doctor if any eye complications are experienced in the interim.

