- Mean MRSE at 4 months postoperative will be compared to target MRSE.
- Frequency and percent of eyes with MRSE within 0.50 D and within 1.00 D of target MRSE at 4 months postoperative will be reported.
- Mean change in total meibomian gland score and mean change in total SPEED score from 3 months to 4 months postoperative will be reported. An increase in both total Meibomian gland score and total SPEED are expected.
- The frequency and proportion of eyes with optical/visual, medical and lens complications will also be reported over time. Rate of adverse events will be reported in the Study and Control groups.

[figure not shown]

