#### 2 ANALYSIS POPULATIONS

#### 2.1 ANALYSIS POPULATIONS

The primary analysis population will be all eyes that are randomized for the precision of biometric measurements, and all eyes that are randomized and implanted for all other analyses. Mean change in total Meibomian gland score will be compared between study group eyes and control group eyes at 1 month postoperatively. All other key study endpoints will be evaluated at 3 months postoperatively. Additional endpoints will be evaluated at 1 month and 3 months postoperatively for the study group and control group and 4 months postoperatively for crossover control group only. Missing data will not be imputed.

Since both eyes of the same subject will be randomized into the same group, eye-specific measurements of same subject are clustered and likely to be positively correlated. As a subset analysis, right and left eyes of subjects will be analyzed for the key eye-specific study endpoints separately to assess for any differences by eye. Demographics/enrollment/accountability data and binocular data will be reported for all randomized subjects with study IOLs successfully implanted.

Version 1.0 1 SAP/DRYE-102-SELF

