Mean monocular BCDVA - (N, Mean, SD, Min, Max, 95% Cl of LogMAR)  Monocular BCDVA by acuity line over time (n and % within each category)	х	eyes
Mean binocular UCDVA, UCIVA, UCNVA, BCDVA - (N, Mean, SD, Min, Max, 95% CI of LogMAR) Binocular UCDVA, UCIVA, UCNVA, BCDVA by acuity line over time (n and % within each category)	х	Subjects
MRSE at 3M - (N, Mean, SD, Min, Max, 95% CI)  Difference between 3M MRSE and target MRSE - (N, Mean, SD, Min, Max, 95% CI)	х	eyes
Contrast acuity at 3M - (N, Mean, SD, Min, Max, 95% CI of LogMAR)	х	Subjects
Mean change in SPEED score from baseline- (N, Mean, SD, Min, Max, 95% CI)	х	eyes
Mean change in total Meibomian gland score from baseline- (N, Mean, SD, Min, Max, 95% CI)	х	eyes

ENDPOINTS EVALUATED at 4-MONTH POSTOP		
Mean monocular BCDVA and UCDVA and change from 3M to 4M - (N, Mean, SD, Min, Max, 95% Cl of LogMAR)	х	Control group eyes only
Monocular BCDVA and UCDVA by acuity line over time (n and % within each category)		
Mean binocular UCDVA, UCIVA, UCNVA, BCDVA and change from 3M to 4M - (N, Mean, SD, Min, Max, 95% CI of LogMAR) Binocular UCDVA, UCIVA, UCNVA, BCDVA by acuity line over time (n and % within each category)	х	Control group subjects only
MRSE at 4M - (N, Mean, SD, Min, Max, 95% CI)  Difference between 4M MRSE and target MRSE - (N, Mean, SD, Min, Max, 95% CI)	х	Control group eyes only
Contrast acuity at 4M and change from 3M to 4M - (N, Mean, SD, Min, Max, 95% CI of LogMAR)	х	Control group subjects only
Mean change in SPEED score from baseline- (N, Mean, SD, Min, Max, 95% CI)	х	Control group eyes only
Mean change in total Meibomian gland score from baseline- (N, Mean, SD, Min, Max, 95% CI)	х	Control group eyes only
RATE OF ADVERSE EVENTS/MEDICAL/LENS FINDINGS		
Type and rate of AE, medical and/or lens findings (n and %)	х	eyes

**KEY**: MGYLS=Meibomian gland yielding liquid secretion, TBUT=tear break-up time, SPEED=standard patient evaluation of eye dryness, MGD=Meibomian gland dysfunction, AC=axial length, ACD=anterior chamber depth, K=keratometric measurements, UCIVA=uncorrected intermediate VA at 66cm, UCNVA=uncorrected near VA at 40cm, UCDVA=uncorrected distance visual acuity, BCDVA=best-corrected distance visual acuity

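### Adverse events are planned as one rate per arm with no period and in implanted eyes only, which mixes LipiFlow, surgical and post-crossover events and omits treated subjects who are never implanted

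*Protocol*

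**What the plan says.** **Analysis.** SAP 4.2.4 states: "The type and rates of adverse events will be summarized for both study group eyes and control group eyes". No visit, period or cut-off is named. The preceding sentence does refer to time, but for a different set of outcomes: "The frequency and proportion of eyes with optical/visual, medical and lens complications will be reported over time". SAP Appendix I has a single row for all of these ("Type and rate of AE, medical and/or lens findings (n and" %), by arm, at eye level. Protocol 20.3 agrees: "Rate of adverse events will be reported in the Study and Control groups".

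**Population.** SAP 2.1 uses all randomized eyes for biometric precision and "all eyes that are randomized and implanted for all other analyses". No separate safety population is defined. Protocol 10.7 recognises subjects who are "randomized but does not undergo bilateral LipiFlow treatment (study group) or receive a Symfony lens for various reasons".

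**Collection.** Protocol Appendix B schedules adverse event checks at Preoperative Visit #1, the LipiFlow treatment (Study group only), Preoperative Visit #2, and Months 1, 3 and 4 (Month 4 for Control only). The Operative column carries no mark. At the LipiFlow treatment, Protocol 10.3 says: "The Investigator or designee performs slit-lamp evaluation after LipiFlow treatment to check for any adverse events". Under Protocol 11.3, events are "recorded on the case report form corresponding to the visit during which awareness of the event occurred"; that section does not mention onset date.

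**Timing.** Under Protocol 10.2, Control receives crossover LipiFlow 0–7 days after the 3-month visit and is seen again 4–6 weeks after that treatment. The Study group finishes at Month 3.

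**The concern.** LipiFlow before surgery is what is randomized; cataract surgery is common to both arms. Protocol 17 expects LipiFlow events to be transient eyelid and ocular surface irritation or inflammation, burning, redness and visual disturbance. The same section lists inflammation and worsening of vision among the general risks of cataract surgery. A rate per arm without periods has three weaknesses.

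- **Dilution.** Surgical events enter both arms and widen the interval around any LipiFlow difference. Randomization to first-eye surgery is the only period free of them, and no table shows it.
- **Bias from crossover.** Without a cut-off at Month 3, Control's rate includes events after its own LipiFlow treatment and several more weeks of follow-up that the Study group does not have.
- **Bias from the population.** A subject treated with LipiFlow before surgery who is never implanted falls outside the analysis, together with any event that followed the treatment.

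A report of similar adverse event rates in the two arms would then say little about LipiFlow.

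**Working it through.** **Figures in the plan.** The documents give no adverse event rate for either device, so there is no safety figure to reproduce. The only number borrowed is the enrolment target in SAP 5: 55 / (1 − 0.20) = 68.75, hence 69 per group, which agrees with the plan.

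**Assumed inputs (subject level, events in different periods independent).**
- Risk between randomization and surgery: 8% Study, 1% Control.
- Surgical-phase risk to Month 3: 25% in both arms, varied from 15% to 35%.
- Crossover LipiFlow risk in Control: 8%.

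**Formulas.** Combined risk = 1 − Π(1 − p) over the periods included. 95% half-width = 1.96 × √[(p₁(1 − p₁) + p₀(1 − p₀)) / 69].

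**Before surgery.** Difference = 8.0 − 1.0 = 7.0 points. Half-width = 1.96 × √[(0.0736 + 0.0099) / 69] = 6.8 points.

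**Pooled to Month 3.**
- Study: 1 − 0.92 × 0.75 = 31.0%.
- Control: 1 − 0.99 × 0.75 = 25.75%.
- Difference 5.25, i.e. 5.3 points. Half-width = 1.96 × √[(0.2139 + 0.1912) / 69] = 15.0 points.

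**Pooled to study end.**
- Study: still 31.0%.
- Control: 1 − 0.99 × 0.75 × 0.92 = 31.7%.
- Difference −0.7 points. The excess has gone, through bias and not only through noise.

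**Sensitivity to the surgical risk.**

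| Surgical risk | Difference to Month 3 (points) | Half-width | Difference to study end |
|---|---|---|---|
| 15% | 6.0 | 13.0 | −0.8 |
| 25% | 5.3 | 15.0 | −0.7 |
| 35% | 4.6 | 16.2 | −0.6 |

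**Sensitivity to the LipiFlow risk.** With Study at 5% or 3% before surgery and Control still at 1%, the pre-surgery difference is 4.0 points (half-width 5.7) or 2.0 points (half-width 4.7). Two-sided Fisher power at 0.05 for the pre-surgery table is 31%, 7% and 1% at Study risks of 8%, 5% and 3%. At 8%, pooling to Month 3 lowers it from 31% to 8%. The plan specifies no test of adverse event rates, so interval width is the more relevant measure.

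**Filing rule.** An event noted at the LipiFlow visit or at Preoperative Visit #2 goes on a pre-surgery form. One that starts after Visit #2 and before surgery can be filed on a postoperative form, because no check is scheduled at the operative visit. Classifying by onset date avoids this.

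**The case against.** **The plan never says that events are pooled over the whole study.** True. A reader might infer that pooling is prescribed, but it is only what one row with no period leads to. The gap is that nothing in the SAP specifies any other table.

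**The arms differ by LipiFlow well beyond surgery.** Also true. A reader might take the pre-surgery window as the only period in which LipiFlow separates the arms. Both arms have the same surgery and Control is untreated until after Month 3, so the randomized difference runs to Month 3. What is special about the early window is only the absence of surgical events.

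**The pre-surgery window is not a perfectly clean comparison.** This stands. Study subjects may have up to one week more before Visit #2, and they have an adverse event check that Control lacks. The table must state time at risk and separate the events found at that check.

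**LipiFlow events are not lost.** Largely fair. Visit forms, the separate form for serious and device-related events, and the causality grades in Protocol 11.4 allow many to be recovered. However, no table by visit or by relatedness is planned, causality is graded against the study device without separating LipiFlow from the lens, and the study is not masked.

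**Misfiling concerns few events.** Agreed. It needs onset between Visit #2 and surgery, for events expected to be transient, and unscheduled visits have their own form. The case report forms are not in the documents, so silence in 11.3 does not show that onset date is uncollected.

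**The size is assumed and the new table has low power.** Both are true. The example shows direction and mechanism, not an expected result.

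**Conclusion.** The point holds as a gap in the safety analysis plan. SAP 4.2.4 and Appendix I specify one adverse event rate per arm, with no period, in randomized and implanted eyes. Applied literally, this dilutes any LipiFlow excess with surgical events, biases the comparison by counting Control's post-crossover experience against Control, and omits treated subjects who are never implanted. The crossover is the more serious of the two timing problems: on the assumed risks, pooling to Month 3 shrinks 7.0 points (half-width 6.8) to 5.3 (half-width 15.0), while pooling to study end reverses the sign (31.0% vs 31.7%).

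These sizes rest entirely on assumed subject-level risks and independence between periods; the SAP counts eyes, and the documents give no rates. They do not support the stronger conclusion that LipiFlow events are irretrievably hidden, since most of the data needed for a split by period appear to be collected already.

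**What to change.** In SAP 4.2.4 and Appendix I, tabulate adverse events by onset date in three periods:

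1. **Randomization to first-eye surgery**, all randomized subjects, by arm, with time at risk stated. List events found at the Study-only LipiFlow visit apart from those found at Preoperative Visit #2.
2. **First-eye surgery to the 3-month visit**, before any crossover treatment, by arm.
3. **After crossover LipiFlow**, Control only, kept out of the between-arm comparison.

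Confirm that the case report form records onset date, and say so in Protocol 11.3, so that the period does not depend on the visit at which the site became aware.

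Cost: one additional descriptive table and, if onset date is not already collected, one field. No new visits or procedures. The table will have low power for rare events and should be read through its intervals.
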